## 7. STATISTICAL CONSIDERATIONS

---

The statistical design of the trial has been performed by [name], University of Texas MD Anderson Cancer Center Adjunct Professor of Statistics, Associate Vice Provost, Adjunct Professor of Biostatistics, Professor of Biostatistics, Biostatistics, Regular Member of the Graduate Faculty.

The proposed study is a proof of concept protocol to evaluate the outcome of patients who receive triple therapy and to evaluate through a retrospective analysis, the clinical utility of the SIMS algorithm and integrated genomic/transcriptomic analysis. For the selected triple combination therapy, we will incorporate a seamless Phase 1/2 design with a limited Phase 1 run-in to determine the recommended Phase 2 dose for the regimen. Patients enrolled in the phase 1 study who receive the RP2D will also be included in the phase 2 efficacy assessment. In the first part of the phase 2 study, up to 100 patients will receive the triple combination therapy and all will have dual biopsies in order to obtain the full set of genomic and transcriptomics data resulting from the investigation of matched tumor and normal biopsies. The population for analysis of response (evaluable patients) will be those that received at least one cycle of treatment. The SIMS algorithm will not be used prospectively to assign patients to treatment. However, it is expected that the SIMS score for each patient will be available within 3 months after the treatment start date. SIMS algorithm will be used retrospectively for defining patient subgroups and correlation correlating with treatment outcome. Patients will be stratified into the fully matched group (Arm A) with all three interventional points activated, or partially matched group, with one or two interventional points activated (Arms B1-B3, C1-C3) or the non-matched group (Arm C4) (see study schema). In addition, after completion of the clinical trial, a correlation study will be performed between patients' clinical outcomes and the predicted match determined by SIMS and all potential prognostic and predictive variables. The primary endpoint for this study is defined as the 6-month objective response rate (by RECIST 1.1 criteria as percent of patients achieve complete response, or partial response). We choose the 6-month response rate for an early efficacy read of the triple therapy. Other efficacy endpoints may include best overall response rate, progression-free survival (PFS), overall survival (OS). The expected result is a better clinical outcome in the fully matched patients arm (arm A) as compared to the partially matched or the non-matched patients' arms.

Also we will compare the estimated numbers of patients in each of the arms as predicted by SIMS versus the observed distribution in the patients treated. Based on previous data published (1), the estimated match in PD-L1 positive (50 patients) is:

- Arm A: Fully matched group, with all three activated targets, will be seen in 10 patients.
- Arms B1 or B2: Partially matched group, with two activated targets (anti PD-L1 + CDK4/6 or anti PD-L1 + anti VEGFR), will be seen in 13 patients and 12 patients respectively.
- Arm B3: Remaining 15 patients will only be matched to anti PD-L1.

For the PD-L1 negative patients (50 Patients), they are further grouped into the following 4 subgroups:

- Arm C1: Partially matched group with two activated targets (CDK4/6 and VEGFR), will be seen in 11 patients.

- Arm C2 or C3: Partially matched group with one activated targets (VEGFR or CDK4/6), will be seen in 8 and 16 patients, respectively.
- Arm C4: Non-matched group, with none of the three activated target matched, will be seen in 15 of patients.

It is expected that half of the patients will be PD-L1 positive and half of the patients will be PD-L1 negative. The hypothesized 6-month response rate in Arm A (fully matched) is 50%; in Arms B1, B2, and C1 (partially matched with two targets) is 40%; in Arm B3 (matched with PD-L1 only) is 30%; in Arms C2 and C3 (partially matched with VEGFR or CDK4/6) is 20%; and in Arm C4 (non-matched group) is 10%. The expected 6-month response rate is 30% in the entire group assuming the triple therapy works.

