**SPRING** trial will aim to enroll patients who are usually offered first line platinum-based chemotherapy. Patients with **documented** targetable driver alterations (EGFR mutations, ALK rearrangements, ROS1 and MET exon 14 skipping mutations) will be excluded. This population currently, without actionable oncogenic driver mutations, envisioned for the enrollment in SPRING trial represents the majority of patients with metastatic NSCLC (~80% in the Caucasian population).

Although the triple combination includes an immunomodulator (avelumab, anti PD-L1), patients will be included regardless of their PD-L1 expression status. Nevertheless, all molecular data available at enrollment will be recorded including PD1 and PD-L1 testing using any of the available IHC tests. Subsequently, the activation status of PD1 or PD-L1 will be assessed through the 1 to 10 SIMS scoring (where 5 is the cut-off), and will be used retrospectively for correlations with clinical outcome and any previous PD1 or PD-L1 tests.

We estimate that overall 85% of the patients treated in the trial will have a profile that is matched to at least one out of the three drugs: 10% matched with three drugs, 36% matched with two drugs and 39% matched with one drug.

SPRING trial phase 2 is intended in first therapeutic line of metastatic NSCLC. Indeed, due to the current extensive use of checkpoint inhibitors (e.g. anti-PD-1, anti-PD-L1) in first line of metastatic NSCLC, any testing of the tri-therapy in subsequent lines would make the enrollment extremely difficult, if not impossible. In addition, following the analogy with AIDS and tuberculosis for which only tri-therapy demonstrated long term efficacy, it would be conceptually difficult to prescribe first an immunomodulator as a monotherapy followed in second line by the tri-therapy, including the immunomodulator. Indeed, we can hypothesize that monotherapy will likely select for resistant clones that would hamper the treatment efficacy and compromise the clinical outcome.

Nevertheless, patients with one to a maximum of 2 prior systemic regimens in the metastatic setting will be accepted for enrollment in phase 1.

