### 1.4. SPRING STUDY SCHEMA

Refer to [Figure 2](#) below.

The trial design is a two-part, multiple parallel cohort, dose-finding and activity-estimating study. The study will enroll patients with metastatic NSCLC that have no targetable alterations (EGFR mutations or ALK translocation) and for whom targeted therapies are not recommended. In the first Phase 1 portion of the trial, patients may have received a maximum of two prior therapies for

metastatic NSCLC but in the second portion of the trial, ONLY patients who have not received prior systemic therapy in the metastatic setting will be included. All patients included must be ECOG 0-1. All patients must consent to a dual biopsy of the tumor tissue obtained from a metastatic lesion under radiologic guidance or from the primary tumor, and of normal matched tissue (bronchial mucosa), obtained through bronchoscopy under video guidance. The paired biopsy samples will be processed in a centralized facility for comprehensive analyses including genome sequencing and transcriptomics (mRNA and miRNA).

The primary objectives of the Phase 1 portion of the trial will be to establish the safety, tolerability, dose-limiting toxicities (DLTs), maximum tolerated doses (MTDs), and RP2Ds of the three drugs, administered concurrently, through enrollment in sequential dose-escalating.

**Figure 2:** Study design and planned retrospective analysis of the clinical utility of the SIMS algorithm and integrated genomic/transcriptomic analysis.

The statistical design of the trial has been performed by [name], University of Texas MD Anderson Cancer Center, Adjunct Professor of Statistics, Associate Vice Provost, Adjunct Professor of Biostatistics, Professor of Biostatistics, Biostatistics, Regular Member of the Graduate Faculty.

We estimate that we will treat up to 100 patients in the first part of phase 2 with futility early stopping rules.

For the first cohort of 100 patients it is expected that half of the patients will be PD-L1 positive and half of the patients will be PD-L1 negative. The hypothesized 6-month response rate in Arm A (fully matched) is 50%; in Arms B1, B2, and C1 (partially matched with two targets) is 40%; in Arm B3 (matched with PD-L1 only) is 30%; in Arms C2 and C3 (partially matched with VEGFR or CDK4/6) is 20%; and in Arm C4 (non-matched group) is 10%. The expected 6-month response rate is 30% in the entire group assume the triple therapy works.

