### 3.3. SPRING STUDY DESIGN

For the triple combination tested, we will conduct a seamless Phase 1/2 trial to establish the safety of the regimen and to identify the recommended Phase 2 dose.

#### 3.3.1. The Phase 1

A Phase 1 study will be conducted to assess the safety of the triple combination and establish concentration of each of the agents:

All patients enrolled in the Phase 1 of the study will be treated with the tested combination until progression unless toxicity occurs earlier. Eligible patients will be those with advanced/metastatic disease NSCLC with a maximum of two prior lines of treatment. Patients with already documented druggable oncogenic aberrations (EGFR mutations, ALK rearrangements, ROS1 or MET exon 14 skipping mutations if available) will be excluded from the trial. All patients with adenocarcinoma histology must have documentation of results for druggable oncogenic aberrations (EGFR mutations, ALK rearrangements, and ROS1 when available) prior to enrollment on the study.

In the case of patients already treated on SPRING protocol who are later determined to have EGFR mutation or ALK translocation or ROS1 or MET exon 14 skipping mutations after SIMS analyses, they will be asked to re-consent.

Patients enrolled in the phase 1 study who receive the RP2D will also be included in the phase 2 efficacy assessment. All patients will undergo a tumor and normal tissue biopsy in order to obtain correlative genomic and transcriptomic data.

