- Any other Grade 3 or Grade 4 non-hematological toxicity that are considered at least possibly related to a study drug and clinically significant after discussion at CMC with exceptions listed below:  
grade 3 nausea, vomiting, diarrhea, that responds to maximal supportive treatment(s) within 3 days, grade 3 liver enzyme elevation, including ALT/AST/GGT that returns to Grade  $\leq 1$  or baseline prior to the time for the next treatment cycle.
- Allergic reactions that necessitate discontinuation of the study drug responsible for the reaction.
- Any Grade  $\geq 2$  pneumonitis of any duration.

- **Hematological dose-limiting toxicity is defined as:**

- Grade 4 neutropenia (absolute neutrophil count, ANC) for  $> 7$  days
- Platelet count  $< 10,000/\text{mm}^3$  one time or bleeding requiring transfusion
- Toxicity that causes a delay of  $> 14$  days between treatment cycles
- Febrile neutropenia despite G-CSF secondary prophylaxis
- Either isolated or recurrent (i.e., cardiac, renal, neurologic) toxicity that is judged by the Investigator to be a DLT.

- **Further evaluation of the combination's toxicity at a dose level:**

Up to 3 additional patients could be added at a dose level to explore the toxicity on an occasional basis after discussion with the CMC. All additional patients will be included in the study's assessment.

- **To decide for dose-escalation cohort at a higher dose level,** the CMC that includes the study investigators and the sponsor clinical study team, will review available data (e.g. safety profile). Subsequent safety reviews by the CMC will be conducted prior to enrollment of patients in a new cohort and to establish the RP2D.

- **Intra-patient dose escalation:**

Patients will be permitted to have a dose escalation to the highest dose shown to be safe at the time of escalation, provided they have no clinically relevant drug-related toxicity  $>$  Grade 1 at the dose

level they are on and that both they and their physician deem a dose escalation to be in their interest. For a dose level to be considered proven safe, there must be at least three patients treated at that dose level for at least four weeks, and the clinical monitoring committee must have deemed that dose level to be at or below the MTD.

- **Dose reduction**

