**For phase 1 and phase 2:**

- Age: Men and women aged  $\geq 18$  years,
- Signed written informed consent,
- Any histologic type of locally advanced or metastatic NSCLC,
- Life expectancy of  $\geq 12$  weeks,
- Measurable or evaluable (cytologically or radiologically detectable disease such as ascites, peritoneal deposits, or lesions which do not fulfill RECIST 1.1 criteria for measurable disease) lesions according to RECIST 1.1 criteria for phase 1 portion. For phase 2, all patients must have RECIST 1.1 measurable disease,
- PHYSIOLOGIC FUNCTION:
  - ✓ Hematologic: Absolute neutrophil count (ANC)  $\geq 1.5 \times 10^9/L$ , platelet count  $\geq 100 \times 10^9/L$ , and hemoglobin  $\geq 9$  g/dL (may have been transfused),
  - ✓ Hepatic: Total bilirubin level  $\leq 1.5 \times$  the upper limit of normal (ULN) range and AST and ALT levels  $\leq 2.5 \times$  ULN,
  - ✓ Renal: Estimated creatinine clearance  $\geq 30$  mL/min according to the Cockcroft-Gault formula (or local institutional standard method).
- PREGNANCY AND CONTRACEPTION:
  - ✓ Pregnancy test: Negative serum or urine pregnancy test at screening for women of childbearing potential.
  - ✓ Contraception: Highly effective contraception for both male and female subjects throughout the study and for at least 90 days after last treatment administration if the risk of conception exists.
- Ability to comply with protocol requirements,
- Willingness to consent and ability to undergo a trucut biopsy to obtain a fresh metastasis or primary tumor biopsy, and to undergo bronchoscopy to obtain a biopsy from normal bronchial mucosa,

- No serious or medically uncontrolled concomitant conditions that are likely to make the patient unfit for SPRING combination therapy, as per investigator assessment,
- ECOG performance status of 0 to 1.

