#### **4.2. EXCLUSION CRITERIA**

***Note: Exclusion criteria should be verified between consent and registration (28 days maximum window).***

- Patients with documented oncogenic aberrations at enrollment: EGFR, ALK, ROS1 when available, MET exon 14 skipping when available. For squamous undifferentiated cell carcinoma, documentation of these aberrations is not mandatory.

Note: For Phase 1 portion, all patients with adenocarcinoma histology must have documentation of results for druggable oncogenic aberrations (EGFR mutations, ALK rearrangements, and ROS1 when available) prior to enrollment on the study.

- For Phase 1 portion, >2 lines of prior therapy in the metastatic setting.
- For the dose escalation phase of the study or until the MTD for the combination regimen has been determined, patients with moderate hepatic impairment defined as AST, ALT, ALP >5 times ULN, which would be grade 3 or higher. However, patients with liver metastases with AST/ALT ≤ 5 x ULN can be included in the study.
- For Phase 2 portion, any prior therapy in the metastatic setting.

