assessment). Target lesions at screening/baseline must have a unilateral tumor measurement of at least 2 times the size of the CT/MRI scan interval cut. The longest diameters for all target lesions will be recorded and a sum of the longest diameter (LD) for all target lesions will be calculated and reported as the baseline sum LD. At baseline, all measurable lesions up to a maximum of 5 lesions per organ systems and 10 lesions in total should be identified as target lesions, ideally representative of all involved organs.

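### Phase 1 patients treated at the RP2D count in the phase 2 response endpoint and the early futility looks even if they fail the phase 2 entry criteria

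*Combined protocol and SAP*

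**What the plan says.** Sections 1.1, 3.3.1 and 7 all carry the pooling rule: "Patients enrolled in the phase 1 study who receive the RP2D will also be included in the phase 2 efficacy assessment". None of them adds a condition.

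The two phases recruit different patients.

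- **Prior therapy.** Section 1.1 says "patients with one to a maximum of 2 prior systemic regimens in the metastatic setting will be accepted for enrollment in phase 1", and section 3.3.1 says "Eligible patients will be those with advanced/metastatic disease NSCLC with a maximum of two prior lines of treatment". For phase 2, section 1.4 says "ONLY patients who have not received prior systemic therapy in the metastatic setting will be included", and section 4.2 lists as an exclusion "For Phase 2 portion, any prior therapy in the metastatic setting".
- **Measurability.** Section 4.1 lets phase 1 patients enter with disease that is evaluable but not measurable, then adds "For phase 2, all patients must have RECIST 1.1 measurable disease".

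The response population in section 7 requires only one cycle of treatment. Section 5.8 adds scan timing, but nothing on prior lines or measurability. Both futility rules (sections 1.4 and 7.2.1) count patients treated at the RP2D, not patients enrolled in phase 2. Section 7.2.1 gives early-stopping probabilities of 0.95, 0.31 and 0.04 at whole-group response rates of 10%, 20% and 30%.

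**The concern.** The primary 6-month CR/PR rate can include patients whom the phase 2 criteria exclude. Some may have no target lesions, and section 5.8 builds response on a baseline measurement: "a sum of the longest diameter (LD) for all target lesions will be calculated and reported as the baseline sum LD". Without that sum there is nothing on which to measure a partial response.

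Timing matters more than numbers. Phase 1 comes first, so its RP2D patients should be the first ones counted. The 14- and 20-patient looks then rest partly on people outside the target population. If those people respond less often, the looks lean toward stopping a regimen that reaches its 30% target in first-line patients. Section 1.1 gives a reason to expect this: it defends first-line testing by hypothesizing that earlier immunotherapy alone would select resistant clones and weaken the triple therapy. No section plans an analysis without these patients, and the stated stopping probabilities do not allow for a mixed population entered in this order.

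**Working it through.** **Inputs from the documents**

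- Stop if responses are at or below 0/14, 2/20, 3/30, 5/40, 6/50, 7/60, 9/70, 11/80 or 12/90 (section 7.2.1).
- Target response rate 30%, null rate 10% (section 7.2.1).
- Phase 1 patients at the RP2D: three, or six after expansion (section 3.3.1, Important note 1). Section 3.3.1 also says "Up to 3 additional patients could be added at a dose level to explore the toxicity on an occasional basis", which gives up to nine.

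**Inputs assumed**

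- m = number of phase 1 RP2D patients who fail the phase 2 criteria. The documents give only the total at a dose level, so 3, 6 and 9 are upper values for the corresponding cohort sizes.
- q = response rate in those m patients. The documents give none, so a range is shown.
- The m patients are counted first. This is inferred from phase 1 preceding phase 2; the text does not state the order.

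**Method.** Let f(i, x) be the probability of having x responses after i patients without having stopped. Then f(i, x) = f(i−1, x)(1 − p_i) + f(i−1, x−1) p_i, with p_i = q for i ≤ m and p_i = 30% afterwards. At each look, the probability at or below the boundary is added to the stopping probability and removed from f.

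**Step 1: reproduce the plan.** With one common rate of 10%, 20% or 30%, the probability of stopping is 0.955, 0.315 or 0.043. The plan states 0.95, 0.31 and 0.04, so its figures are right for a homogeneous population.

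**Step 2: share of the early looks.** If all three to six RP2D phase 1 patients were ineligible, they would be 3/14 to 6/14 = 21–43% of the first look and 3/20 to 6/20 = 15–30% of the second. These are upper values.

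**Step 3: probability of wrongly stopping when first-line patients respond at 30%**

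| q | m = 3 | m = 6 | m = 9 |
|---|---|---|---|
| 30% | 4.3% | 4.3% | 4.3% |
| 25% | 4.9% | 5.7% | 6.5% |
| 20% | 5.6% | 7.4% | 9.7% |
| 15% | 6.4% | 9.5% | 14.0% |
| 10% | 7.2% | 12.1% | 19.8% |

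With m = 1 or 2, the figures are 4.7% or 5.1% at q = 20%, and 5.1% or 6.1% at q = 10%.

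The chance of passing every look is one minus these values: 95.7% with no effect, 92.6% for m = 6 at q = 20%, and 87.9% for m = 6 at q = 10%.

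**Step 4: where the risk arises.** Take m = 6 and q = 10%. The 14-patient look contributes 0.9^6 × 0.7^8 = 0.031, against 0.7^14 = 0.007 with none. The 20-patient look contributes 0.080, against 0.030. Together that is 0.111 of the total 0.121.

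**Step 5: order or dilution?** Six patients at 10% among 100 give a pooled rate of (6 × 10% + 94 × 30%)/100 = 28.8%. A common rate of 28.8% gives a stopping probability of 5.5%; the same six patients entered first give 12.1%. Order is the main driver.

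**Step 6: effect on the final estimate.** At q = 10% the pooled rate is 29.4% (m = 3), 28.8% (m = 6) or 28.2% (m = 9). With 10% of patients expected in Arm A, three to six such patients put 0.3 to 0.6 of a patient there.

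**The case against.** The pooling is deliberate. It is stated three times within a design described as seamless, and nothing in the plan is miscalculated. Both inputs that create the harm are missing from the documents: there is no response rate by prior line or measurability, and no count of ineligible patients. Some phase 1 patients at the RP2D may be untreated with measurable disease. Double-digit false stopping needs about six ineligible patients responding at about 10%, which is the plan's own null rate, or nine at just under 20%. The formal test in the fully matched arm is almost untouched.

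The plan also softens the consequence. Section 7.2.1 makes stopping permissive and provides for discussion when a subgroup looks active. Section 3.1 calls the first 100 patients exploratory. Section 7.6 plans intent-to-treat and per-treatment analyses, and section 7 plans correlation of outcome with prognostic variables.

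The points on size and on the final estimate stand. The mitigation is only partial. For the second futility rule, section 1.4 makes stopping firm where section 7.2.1 makes it permissive, and that rule's 20-patient look carries most of the risk. The subgroup discussion is reserved for rare cases. Neither the section 7.6 analyses nor the prognostic correlation names prior line or measurability, and neither alters who is counted at a look.

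**Conclusion.** The concern holds. The text lets patients who fail the phase 2 criteria into the phase 2 response endpoint and the futility counts, and no other provision removes them. The published stopping probabilities are correct only for a population with one response rate.

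The harm is conditional. It needs a lower response rate in these patients and their entry ahead of the phase 2 patients. Under those assumptions, false stopping at a true 30% goes from 4.3% to 5.6–7.4% with three to six such patients at 20%, and to 7.2–12.1% at 10%. With one or two such patients it stays at about 5–6% or below, and with equal response there is no effect. The final estimate and Arm A are barely affected; the exposure is at the 14- and 20-patient looks. The change should be made, though the flaw does not invalidate the design.

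**What to change.** In sections 1.1, 3.3.1 and 7, state that the primary 6-month response endpoint and both futility rules count only RP2D patients who meet the phase 2 entry criteria, including phase 1 patients who qualify. Put the same sentence in section 1.4, which repeats the futility rules. Refer to the criteria in sections 4.1 and 4.2 rather than restating them, because sections 1.4, 3.3.2 and 4.2 word the prior-therapy condition differently. Report the remaining phase 1 RP2D patients separately or in a sensitivity analysis that adds them back, and keep them in all safety analyses. Also say whether a phase 1 patient who reaches the RP2D by intra-patient escalation counts as having received it for the efficacy assessment.

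The cost is one sentence in each section. The efficacy set loses up to about nine patients (possibly more if escalated patients were meant to count), and the 14- and 20-patient looks come slightly later. In return, the counted patients match the trial's intended population, so the stopping probabilities in section 7.2.1 are no longer distorted by this pooling.

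If the sponsor prefers to keep the pooling, the alternative is to say so, recalculate the operating characteristics for the mixed population in its entry order, and report the results with and without these patients.
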